The preliminary phase of the study will comprise completion of medical and dental histories, signing of consent forms, obtaining radiographs and photographs, performing screening assessments to confirm eligibility, and instruction in oral hygiene techniques. Before the periodontal surgical procedure, subjects may undergo plaque removal, then root planing and scaling to the areas to be treated, if such treatment is indicated. The final esthetic outcome of the treated sites will be evaluated by the patients using the Visual Analog Scale (VAS) ranging from "Very Unsatisfied" to "Very Satisfied" (before and after viewing baseline photos). Other clinical assessments will include: subject pain/discomfort questionnaire, change in probing depth, change in clinical attachment level, change in width of keratinized tissue from baseline to 6 and 12 months and change in radiographic bone gain and pathology. Digital photographs will be obtained at each study visit and radiographs of the test sites will be made at the baseline, 6 and 12 month visits.

The primary efficacy parameters will include:

- Esthetic satisfaction from baseline to six months of all treated areas, as assessed by both the examiner and the subject using the Visual Analog Scale (VAS), prior to and after viewing baseline photos
- Subject pain/discomfort questionnaire
- Change from baseline in probing depth (PD) measured from the mucosal margin to the bottom of the probeable pocket

- Gingival recession (Rec) measured from the implant platform (IP) to the mucosal margin
- Change from baseline visit in clinical attachment level (CAL) measured from IP to the bottom of the probeable pocket
- Change from baseline in width of the keratinized tissue (KT)
- Change from baseline in radiographic a) bone gain; b) pathology

INVESTIGATIONAL DEVICE

GUIDOR® easy-graft® CLASSIC

GUIDOR® easy-graft® CLASSIC is bone grafting system contains: syringe containing betatricalcium phosphate (β -TCP) granules coated with poly (lactide-co-glycolide) (PLGA) and ampule containing BioLinker® Activator (N-methyl-2-pyrrolidone and water).

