3.2.1 Primary Efficacy Endpoints

- Change from baseline in probing depth
- Change from baseline in clinical attachment level
- Change from baseline in width of the keratinized tissue
- Change from baseline in radiographic a) bone gain; b) pathology
- Esthetic satisfaction from baseline to six months of all treated areas, as assessed by both the examiner and the subject using the Visual Analog Scale (VAS), prior to and after viewing baseline photos

- Subject pain/discomfort questionnaire

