3.6 Schedule of Investigational Events

3.6.1 Screening Visit (Visit 1)

At the screening visit the following procedures and assessments will be performed within 32 days prior to surgery:

- Informed Consent
- Subject registration
- Medical history collection and physical examination:
 - Record of past therapy
 - Urine pregnancy test (females of child-bearing potential only)
 - Medications
- Dental history collection
 - Record of past therapy
- Screening assessments to determine eligibility:
 - O'Leary Plaque Index
 - Probing depths
 - Implant mobility,
 - Clinical attachment level
 - Obtain baseline radiographs of study sites
- Dental cleaning

- Oral hygiene instruction
- Supragingival plaque control, as appropriate
- Examiner and subject baseline esthetic satisfaction VAS assessments
- Radiographs of all target study sites

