3.6.2 Baseline/Treatment (Visit 2)

Visit 2 may occur concurrently with Visit 1. If separate visits are to occur, Visit 2 must occur within 32 days of the screening examine.

- Examiner calibration (for first 2 subjects enrolled only)
- Preoperative and Intraoperative digital photographs
- Concomitant medications
- Surgical procedure
- Post-operative instructions
- Collection of any Adverse Events

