3.6.3 Post op - Week 1 (Visit 3)

- An Investigator will rate and record the judgment of healing
- Study personnel will obtain clinical photographs of surgical sites taking care not to place apical tension on flap

- Post-operative instructions (e.g. Chlorhexidine rinse) and pain management according to standard procedures
- Complete Pain Rating Scale
- Rate and record color and texture of treated areas
- Adverse event review
- Concomitant medication review
- Suture removal according to healing
- Measurement of width of keratinized tissue
- Pain Medication review

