After the flaps have been raised and the area debrided, characterization of the morphology and measurements of the defects are made, with the UNC 15 periodontal probe, and recorded as follows:

Alveolar Bone Level (Before and after osteoplasty if needed)

Notation of intra marrow penetration of alveolar crest

Notation of alveolar crest topography and whether osteoplasty was to be performed to refine contours.

Clinical Photographs

Clinical photographs will be taken of each tooth involved in the study before, during and after surgery, at Weeks 1, and 6 post surgery and at the 3, and 6 month follow-up examinations.

Post-Op Discomfort and Satisfaction Questionnaires

The subject's satisfaction with respect to postoperative discomfort between test and control quadrants will be evaluated by asking the subject about pain, bleeding, swelling and sensitivity using 10 cm visual analogue scale (See Appendix 1).

Procedure/ Assessment	Visit 1	Visit 2	Visit 3	Visit 4	Visit 5	Visit 6	Visit 7
	Screen 0-32 Days	Prior Surgery	Day 0	Post-op Day 7	1 Month 42± 7 Days	Month 3 90± 14 Days	Month 6 ±14 Days
Informed Consent	X						
Eligibility/ Study Lesion Identification, Subject Registration	X						
Demographics/Dental/Medical History	X						
O'Leary Plaque Index	X					X	X
Probing Depths	X					X	X
Pregnancy Test	X ¹						
Radiographic Exam	X					X	X
Dental Cleaning	X				X	X	X

CONFIDENTIAL AND PROPRIETARY INFORMATION OF Creighton University School of Dentistry Department of Periodontics

Protocol Number: CUSD2

Original Issue Date: January 6th 2017

Digital Photos		X	X	X	X	X	X
Examiner and Subject GORS and VAS of esthetic satisfaction		X	X	X	X	X	X
Plaque Control/Oral Hygiene Instruction	X	X	X	X	X	X	X
Concomitant Medications	X	X	X	X	X	X	X
Adverse Events		X	X	X	X	X	X
Clinical Attachment level	X					X	X
Examiner calibration		X					
Easy Graft Classic surgery		X					
Second stage surgery for submerged implants only						X	
Rate and record Judgment of Healing			X	X	X	X	X
Pain Rating Scale			X	X	X	X	X
Color and Texture			X	X	X	X	X
Width of Keratinized Tissue				X	X	X	X

1. In females of child-bearing potential only

CONFIDENTIAL AND PROPRIETARY INFORMATION OF Creighton University School of Dentistry Department of Periodontics

Protocol Number: CUSD2

Original Issue Date: January 6th 2017

Page 43 of 63

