APPENDIX I: QUESTIONNAIRES/SURVEYS

1. Examiner's Judgment of Healing
2. Pain Visual Analogue Scales
3. Discomfort and Satisfaction Questionnaire
4. Color and Texture Scale
5. Inflammation Score

EXAMINER'S JUDGMENT OF HEALING

(circle response)

Upper Right Quadrant:

Much worse than expected	Worse than expected	As Expected	Better than expected	Much better than expected
--------------------------	---------------------	-------------	----------------------	---------------------------

Upper Left Quadrant:

Much worse than expected	Worse than expected	As Expected	Better than expected	Much better than expected
--------------------------	---------------------	-------------	----------------------	---------------------------

Lower Right Quadrant:

Much worse than expected	Worse than expected	As Expected	Better than expected	Much better than expected
--------------------------	---------------------	-------------	----------------------	---------------------------

Lower Left Quadrant:

Much worse than expected	Worse than expected	As Expected	Better than expected	Much better than expected
--------------------------	---------------------	-------------	----------------------	---------------------------

PAIN VISUAL ANALOGUE SCALES

Please have patient complete the scales below by drawing a single vertical line across each scale at the point corresponding to the patient's level of pain.

Upper Right Quadrant

No Pain

Extreme Pain

Upper Left Quadrant

No Pain

Extreme Pain

Lower Right Quadrants

No Pain

Extreme Pain

Lower Left Quadrant

No Pain

Extreme Pain

DISCOMFORT & ESTHETIC SATISFACTION QUESTIONNAIRE: Maxillae

Category	Right Quadrant	Left Quadrant
Sensitivity	None Mild Moderate* Severe* Duration: _____	None Mild Moderate* Severe* Duration: _____
Bleeding	None Mild Moderate* Severe*	None Mild Moderate* Severe*

	Duration: _____	Duration: _____
Swelling	None	None
	Mild	Mild
	Moderate*	Moderate*
	Severe*	Severe*
	Duration: _____	Duration: _____

(*Record as Adverse Event)

Has the patient experienced any other differences between the Left and Right Study sites?

Y N

If Yes, explain: _____

Overall, how satisfied is the patient with the **appearance** of the study sites?

Right Study Site

Very Satisfied Satisfied Neither Unsatisfied Very Unsatisfied

Left Study Site

Very Satisfied Satisfied Neither Unsatisfied Very Unsatisfied

If not satisfied, please explain: _____

Overall, which side did the patient experience the most discomfort? Right Left

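### Pain is a primary efficacy endpoint, but no pain score is taken before surgery, there is no control arm, and the pain scale states no recall period

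*Combined protocol and SAP*

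**What the plan says.** Section 2.0 introduces its list with "The primary efficacy parameters will include", and the pain/discomfort questionnaire is on that list. Section 3.2.1 repeats it as "Subject pain/discomfort questionnaire", and section 3.5.2 lists it again under the primary efficacy assessment. In 3.2.1 the probing, attachment, keratinized-tissue and radiographic items are defined as changes from baseline, and the esthetic item runs from baseline to six months. The pain item has no baseline, time point or comparison.

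The Visit 1 list (3.6.1) has a patient-reported baseline for esthetics, "Examiner and subject baseline esthetic satisfaction VAS assessments", but nothing for pain. The Visit 2 list (3.6.2) includes work done before the incision, such as "Preoperative and Intraoperative digital photographs", but again no pain score. Pain first appears at Visit 3 (3.6.3) as "Complete Pain Rating Scale" and is repeated at Visits 4 to 7. The flowchart in 3.7 agrees: its pain row is marked at Visits 3 to 7 and blank at Visits 1 and 2.

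The pain form in Appendix I has the patient respond by "drawing a single vertical line across each scale at the point corresponding to the patient's level of pain". It does not say whether this means now, on average, or at worst since surgery.

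**The concern.** An efficacy claim about pain needs something to compare the post-treatment score with: the same subject before treatment, or an untreated or differently treated group. This plan schedules neither. A low pain score at 6 or 12 months would be reported under primary efficacy, yet the subject may have had just as little pain before the operation. No inclusion criterion in 3.3.1 requires pain.

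The same instrument also seems meant to describe how well subjects tolerate surgery. For that purpose its first use comes several days after the operation, with no stated period to which the answer refers. Two subjects could mark the line for different periods, and their scores would not be comparable. A baseline that is not collected before surgery cannot be recovered afterwards.

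**Working it through.** The plan gives no sample-size, power or effect-size figure for pain, so there is nothing of that kind to reproduce. The check compares the schedule, the visit windows and the forms.

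**Count of ratings.** Sources: visit lists 3.6.1 to 3.6.7 and the flowchart in 3.7.
- Before surgery (Visit 1, and Visit 2 before the operation): 0.
- After surgery (Visits 3 to 7): 5.

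In the text copy, the flowchart header puts a Day 0 label over the Visit 3 column. Surgery is marked in the Visit 2 column, and both 3.2.3 and 3.6.3 define Visit 3 as week 1. I therefore read this as a split header cell, not as a pain rating on the day of surgery.

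**Timing of the first rating.** Section 3.2.3 sets Visit 3 at week 1 ± 3 days.
- Earliest: 7 − 3 = day 4.
- Latest: 7 + 3 = day 10.
- Ratings scheduled on days 0 to 3: 0.

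**What a late score says about relief.** Let Y0 be the pain score before surgery and Ym the score at month m. Relief is the change Ym − Y0, and Y0 is never observed. Assume the scale is 10 cm long; 3.7 gives that length for the discomfort scales, and I assume it applies to the pain line too. Y0 can then lie anywhere from 0 to 10, so the change can lie anywhere from Ym − 10 to Ym. For Ym = 0, the best possible result, the range is −10 (complete relief of extreme pain) to 0 (no change, because there was no pain). The uncertainty is the full length of the scale for every subject, so a change score is available for 0 of 15. Averaging does not help, because the mean change needs the mean of Y0.

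**Could a comparator replace the baseline?** Section 3.1 describes a case series with one treatment, so no between-group difference exists either.

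**Could another record replace the baseline?** Section 3.4.5 asks for pre-surgical pain medication. That is an indirect sign, not a score on the endpoint's scale.

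**Could another record cover days 0 to 3?**
- The discomfort questionnaire in Appendix I grades sensitivity, bleeding and swelling, each with a duration. It has no pain-intensity item, although 3.7 says that pain will be asked about. No visit list or flowchart row names the form.
- Pain-medication review is listed from Visit 3 onward, and 3.4.5 has the periodontist grade post-surgical pain in three levels. Both carry information, but neither is the endpoint.
- Adverse-event capture is unclear for the first two days. Section 3.2.4 makes an exception for surgery-related events within 48 hours, while section 4.0 collects all events after surgery.

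**The case against.** The strongest reply is that the plan never promises a change in pain. Pain is the one patient-reported item not tied to baseline, and 3.7 presents the questionnaire as a measure of post-operative discomfort. On that view it is a tolerability measure under the wrong heading, and change between post-operative visits can still be computed. This largely stands, and it is why relabelling is an acceptable remedy. It does not rescue the current text, which calls the item primary efficacy in three places.

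A second reply is that a baseline may add little. Acute infectious lesions at the site are excluded (3.3.2), and scaling may precede surgery (3.4.1). Baseline pain may therefore be near zero, which leaves little room for improvement. Without a control arm, even a clear fall could not be attributed to the graft. Both limits are real and should be reported beside any change score. A near-zero baseline would itself be worth knowing, because it would show that low later scores are not relief.

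Three stronger readings may tempt a reader, and the documents do not support them:
- That the first rating measures only pain on that day. The form states no recall period, so what it covers is unknown, not known to be a single day.
- That pain caused by surgery goes unrecorded. A rating on day 4 to 10 can register residual pain, and medication use and the periodontist's grading give indirect evidence. What is missing is a scheduled rating on days 0 to 3 and a way to separate surgical pain from pain already present.
- That the endpoint would look favourable whatever the treatment does. Persistent or recurrent pain at months 3 to 12 would look unfavourable. Section 5.0 sets no test or success rule for pain, and the success definition in 1.0 does not include it.

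**Conclusion.** The point holds in a limited form. As scheduled, the pain endpoint cannot show relief of pain in any of the 15 subjects: there are no ratings before surgery, five after it, and no control arm. For tolerability it is usable but incomplete, since the first rating falls on day 4 to 10, none is scheduled on days 0 to 3, and the period that rating covers is unspecified.

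This rests on reading the flowchart by visit number, which agrees with the visit lists, and on the Appendix I pain scale being the only pain score behind the endpoint. It should be corrected before further subjects are operated on. It does not affect the clinical or radiographic endpoints.

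**What to change.** 1. Add the pain scale at Visit 2 before surgery, in 3.6.2 and in the flowchart. Define the efficacy summary as change from that score to months 6 and 12. State in 5.0 that a near-zero baseline and the absence of a control limit its interpretation as efficacy, and report how many subjects have a baseline score.
2. State the recall period on the pain form. At Visit 3, ask for worst pain since surgery as well as pain today.
3. Report the early post-operative ratings as tolerability, not efficacy.
4. If no baseline is added, move the whole pain endpoint to tolerability in the synopsis, 2.0, 3.2.1 and 3.5.2. This matches the post-operative framing in 3.7.

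The cost is one extra scale at an existing visit and one extra line on the Visit 3 form. The worst-pain item will carry some recall error, which is a small price for information about the first days. No treatment or visit changes.

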3.2.2 Study Duration

The duration of this study is to be twelve (12) months following the surgical procedure.

3.2.3 Study Timeline Summary

Screening	Baseline and Surgery	Post Treatment Evaluation				
Visit 1	Visit 2	Visit 3	Visit 4	Visit 5	Visit 6	Visit 7
Within 32 days of surgery	Day 0	Week 1 ± 3 days	Month 1 ± 7 days	Month 3 ± 14 days	Month 6 ± 14 days	Month 12 ± 14 days

3.2.4 Safety Endpoints

Assessments of subject safety will include a tabulation of the incidence of adverse events.

All treatment-related adverse events that occur up to 30 days excepting surgery related AEs within 48 hours after any treatment will be recorded, and all serious adverse events throughout the study will be recorded.

3.3 Subject Eligibility

3.3.1 Inclusion Criteria

Subjects must meet the following inclusion criteria to be eligible for the study:

1. Subject has read and signed the IRB approved consent form before treatment.
2. Subject must be age 21 or above.
3. Subject must be willing and able to follow study procedures and instructions.
4. Subject affected by moderate to severe peri-implant disease*.
5. Treated chronic periodontitis and proper periodontal maintenance care,

Dental implant must meet the following criteria to be selected for the study:

1. Implant presenting PD \geq 6 mm
2. Radiographic implant bone loss more than 25% of the implant length (Apex of the implant to implant platform)²³.
3. Peri implant bone defect being a buccal dehiscence and semicircular bone resorption to the middle of the implant body, buccal dehiscence and circular bone resorption with lingual bone plate intact or circular bone resorption with buccal and lingual bone plates intact

²³ Froum SJ, Rosen PS. A proposed classification for peri-implantitis. *Int J Periodontics Restorative Dent.* 2012 Oct;32(5):533-40.

CONFIDENTIAL AND PROPRIETARY INFORMATION OF Creighton University School of Dentistry Department of Periodontics

Protocol Number: CUSD2

Revision: October 22nd 2018

Original Issue Date: January 6th 2017

4. Single tooth implant restoration or implant supported fixed partial denture.

3.3.2 Exclusion Criteria

Subject with any of the following will not be eligible for the study:

- Subjects participating (currently or within 30 days prior to enrollment) in other clinical trials involving therapeutic intervention (either medical or dental).
- Subjects with poor oral hygiene as indicated by a score of greater than 50% on the O'Leary Plaque Index.
- Subjects with a systemic condition, which would preclude periodontal treatment, including but not limited to uncontrolled diabetes.
- Subjects with acute infectious lesions in the areas intended for treatment.
- Subjects taking chronic (i.e., > 2 weeks), therapeutic doses of medications known to affect bone metabolism such as nonsteroidal anti-inflammatory drugs or bisphosphonates. Prophylactic aspirin (\leq 325 mg q.d.) for cardiovascular indications will be permitted in subjects.
- Female subjects who are pregnant or lactating, or sexually-active female subjects who are of childbearing potential and are not using hormonal or barrier methods of birth control. (except for when a result of pregnancy test is negative)
- Subjects who are on any chronic antibiotic or steroid therapy.

- Smoker using more than 10 cigarettes or equivalent per day.
- Smoker using cigar, smokeless tobacco use or e-cigarette.
- Subjects diagnosed with drug induced gingival hyperplasia (e.g. calcium channel blockers).
- Subjects with radiographic evidence of pathology in other areas of the mouth besides implant area to be treated.
- Implant mobility.
- Subjects with parafunctional habits and not wearing bite guard.
-

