3.4.2 Study Treatments

Screening will take place no more than 32 days prior to the first treatment and will include the clinical assessments required to confirm eligibility. Informed Consent Form will be signed at Screening Visit (Visit 1). Clinical photograph, radiographs of the implant treated, clinical measurements will be taken and recorded (Pocked Depth, Mucosal Recession, Clinical Attachment Level).

The day of surgery will be designated as Day 0. Subjects will have peri-implant regeneration surgery.

Whenever possible implant crown will be removed and cleaned. Healing screw will be placed on the implant. Upon flap elevation and debridement of the peri implant lesion, the operator will record the type of bony defect associated to the treated implant (see Inclusion criteria 3). Titanium Implant surface will be debrided with rotating burs and brushes (PERI-SET, Sweden&Martina Inc.), and decontaminated with EDTA (PrefGel: Straumann) for 2 minutes and with the alternation of Perio-Flow Chlorhexidine mouthwash (GUM® ParoEx®, Chlorhexidine Gluconate Oral Rinse USP 0,12% SUNSTAR), saline water and H₂O₂ using cotton pellets. After the completion of these procedures, Easy-graft® CLASSIC will be placed on the peri-implant defect surface. GUIDOR® Bio-resorbable Matrix Membrane will be

placed on top of the easy-graft classic and stabilized. If the implant crown was successfully removed, flaps will be primary closed and the implant will be covered completely. Second stage, minimally invasive surgery to gain access to the implant will be performed at 6 months. Intraoperative and postoperative measurements will be made and the flap will be closed with sutures. Patients will be instructed to take 500 mg of amoxicillin three times a day for 7 days, starting at least one hour prior the procedure.

Fifteen (15) male or female subjects, aged 21 to 85 years, will be recruited for the study from existing patient databases, as well as, from screenings of volunteers responding to advertisements, if necessary.

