3.5.5 Laboratory Assessments

The following laboratory assessments will be conducted at screening:

- Urine pregnancy test (females of child-bearing potential only)

CONFIDENTIAL AND PROPRIETARY INFORMATION OF Creighton University School of Dentistry Department of Periodontics

Protocol Number: CUSD2

Revision: October 22nd 2018

Original Issue Date: January 6th 2017

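### The negative-test exception leaves the contraception exclusion with no effect, and no scheduled check confirms the pregnancy exclusion on the day of surgery

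*Combined protocol and SAP*

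**What the plan says.** The exclusion in 3.3.2 has two limbs. The first bars "Female subjects who are pregnant or lactating". The second bars sexually active women of childbearing potential who use neither hormonal nor barrier contraception, and is followed in parentheses by the exception "except for when a result of pregnancy test is negative".

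Section 3.5.5 introduces the pregnancy test with the words "The following laboratory assessments will be conducted at screening". The Visit 1 list in 3.6.1 names the test and who has it: "Urine pregnancy test (females of child-bearing potential only". The schedule table at the end of the Summary of Clinical Assessments marks the test once, in the Visit 1 column.

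On timing, 3.4.2 states: "Screening will take place no more than 32 days prior to the first treatment". Section 3.6.2 lets the surgery visit coincide with screening. If the visits are separate, "Visit 2 must occur within 32 days of the screening examine". The items listed for that visit are examiner calibration, photographs, concomitant medication, the surgery, post-operative instructions and adverse events.

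**The concern.** The protocol treats pregnancy as disqualifying. Two provisions could support that on the day of surgery: a test close to the operation, or a contraception requirement covering the interval after an earlier test. The test is placed at screening, and the exception removes the contraception requirement for anyone whose result is negative. The women most likely to conceive between screening and surgery are therefore those for whom nothing further is asked or scheduled.

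What is at stake is subject protection at the point where the investigational graft and membrane are placed and the perioperative antibiotic course is given. It is a question of whether a stated eligibility rule is verified, and has no bearing on the efficacy estimates.

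**Working it through.** No sample-size, power or error-rate figure bears on this point. The check sets the rule beside the schedule.

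**Step 1: what the contraception limb does.** Take a woman of childbearing potential who is sexually active and uses neither hormonal nor barrier contraception. She is tested at Visit 1 (3.5.5, 3.6.1).

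| Screening result | Pregnant-or-lactating limb | Contraception limb | Outcome |
|---|---|---|---|
| Positive | Excludes her | Applies, but adds nothing | Excluded |
| Negative | Does not exclude her, unless she is lactating | Lifted by the exception | Contraception limb has no effect |

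In neither row does the contraception limb change the outcome. It can exclude nobody who has a test result, and every woman to whom it could apply has one by design.

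**Step 2: when pregnancy is checked.** Section 3.5.5, the Visit 1 list in 3.6.1 and the schedule table all place the test at screening and nowhere else. The column headings of the schedule table do not line up cleanly with the visit numbers, but the mark is in the first column, so this does not alter the reading. The table's eligibility row is likewise marked at Visit 1 only, and the Visit 2 list in 3.6.2 contains neither a test nor a renewed eligibility check.

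**Step 3: how old the result can be at surgery.**
- Minimum: 0 days, because 3.6.2 allows Visits 1 and 2 on the same day.
- Maximum: 32 days (3.1, 3.4.2, 3.6.1, 3.6.2).
- A gap of weeks is a foreseen path. Sections 3.1 and 3.4.1 allow plaque removal and scaling 2 to 4 weeks before surgery, which is 14 to 28 days and fits within 32. They also make plaque and bleeding scores below 20% a condition for operating. The plan thus sets a hygiene condition for surgery to go ahead but schedules no equivalent check for pregnancy.

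**Step 4: the two together.** A woman using no contraception who tests negative at Visit 1 is eligible on this criterion. If she conceives before surgery, or had a pregnancy too early to detect at screening, nothing scheduled would reveal it on Day 0. With same-day visits only the second possibility remains.

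**The case against.** A reader might infer that the pregnancy exclusion cancels itself. It does not: the bar on pregnant or lactating women is untouched, and only the contraception limb is emptied. A reader might also infer that the plan permits treating a subject who is pregnant on Day 0. It does not: a woman known to be pregnant remains ineligible under 3.3.2, and operating on her would breach the protocol. The gap is in detection.

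Other objections carry weight. The interval between test and surgery comes from the schedule and would exist without the exception; a woman using contraception could also conceive in it. The exception widens who is exposed. The parenthesis follows a full stop and does not say which test it means, so its scope is partly a matter of reading. Applying it to the pregnant-or-lactating limb would make no sense, however, and the only test the plan schedules is the one at screening.

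It is tempting to attach a probability by applying a monthly conception rate to the full 32 days. The documents give no such rate, 32 days is the maximum, and the number of women concerned among 15 subjects aged 21 to 85 is not stated.

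Finally, the documents describe no reproductive risk from the graft, membrane or procedure, and the consent pages are not in the text reviewed, so any pregnancy warning or duty to report there cannot be checked or assumed absent. That limits what can be said about harm. It does not answer the narrower point that the protocol's own criterion goes unverified at surgery.

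**Conclusion.** The point holds in this form: the negative-test exception leaves the contraception limb without effect, and the plan has no scheduled check that the pregnancy exclusion still holds on Day 0.

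Its size is an interval of 0 to 32 days between the only test and surgery, for an unknown and possibly empty subset of 15 subjects. No endpoint, estimate or analysis changes.

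The conclusion assumes that the exception refers to the scheduled screening test and attaches to the contraception limb. It is worth correcting despite the small numbers, because a stated exception defeats a stated safeguard when both are followed as written, and the correction is cheap.

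**What to change.** The sponsor and investigator should reconcile 3.3.2, 3.5.5, 3.6.1, 3.6.2 and the schedule table. The text should say which limb the exception qualifies and which test result it relies on. The exception and the timing of the urine test already planned should then together verify the protocol's own pregnancy exclusion at the time of surgery, with the visit lists and the table agreeing. How this is done clinically is for the sponsor and investigator to decide.

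The cost is a few lines of text and at most one repeat dipstick for a few subjects at a visit that already takes place; same-day screening and surgery need no second test. The downside is a rare cancellation on Day 0.
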